5.5 Study Sites

UCLA Integrated Substance Abuse Program (ISAP). The leadership, data management, and analysis portions of the proposed project will occur at UCLA ISAP in Los Angeles.

[name], will be the physician PI for this study. He has extensive experience in both the use of Vivitrol and behavioral treatments. He will be involved in supervision of the medical aspects of this study, randomization, and will meet regularly with other study personnel. He has conducted over a dozen clinical trials using MAT and will be responsible for medical team training. More recently, he has conducted research using Vivitrol and has been instrumental in the training of other ISAP medical personnel on the Vivitrol injection.

For this project, the primary sites for recruitment, data collection, and treatment services are the Bernalillo County Metropolitan Detention Center and the University of New Mexico, Department of Psychiatry.

Bernalillo County Metropolitan Detention Center (BCMDC). Recruitment and induction will occur at the jail sites in the BCMDC System. The jail facility houses sentenced and unsentenced inmates. The types of inmates housed here are general population, violent/assaultive offenders, psychiatric, and inmates needing medical services. This facility is staffed with Sheriff Service Technicians, intake and release specialists, medical service staff contracted by the County Behavioral Health Department, and clerical support staff. Bernalillo County opened the MDC facility in 2003. Currently, the MDC averages about 40,000 bookings per year, with an average daily population of 2,636. Males account for 87% of the inmate population. With regard to race/ethnicity, 54% are Hispanic, 23% White-Non-Hispanic, 12% American Indian, 9% African-American, 0.4% Asian, and 1.7% are categorized as "Other." Currently the MDC detoxifies an average of 758 individuals monthly—412 from alcohol and 346 from opiates.

The University of New Mexico Addiction Substance Abuse Program (ASAP), The University of New Mexico Center on Alcoholism, Substance Abuse, and Addictions (CASAA); These programs will be the locations for post-release assessment and medical management visits. ASAP and CASAA offer a range of treatment services designed to help individuals coping with substance use disorders. Services include screening, crisis intervention, individual, group, and family counseling, HIV/Hep education, assessment, and evaluation, referrals to community-based services, and outreach to the community. Outpatient treatment programs providing psychosocial interventions are located throughout the county. In the community, the MATS program provides comprehensive detoxification, treatment, and transitional housing services for medically indigent

populations in the Albuquerque area. Operated by Bernalillo County, the MATS program has extensive partnerships with other community medical, mental health, alcohol/drug and homeless service agencies. The Addictions and Substance Abuse Program (ASAP) is operated by the UNM Department of Psychiatry and is conveniently located adjacent to the UNM CASAA facility.

6.0 OUTCOME MEASURES

The project emphasizes evaluation of the clinical utility of the Vivitrol pharmacotherapy with and without a PN condition (VI, PNV), as compared to a drug education (DE) condition. Descriptive statistics will provide an overall assessment of the implementation of the protocol.

6.1 Primary Outcome Measure

The primary outcomes will be opioid use and a DSM-5 diagnosis of opioid use disorder 6 months after randomization.

6.2 Secondary Outcome Measures

- HIV risk behaviors (compared using repeated measures procedures to evaluate possible change in sexual and drug-related behaviors that may inhibit or promote HIV infection) measured by the HIV-GAIN;
- (2) Self-reported number of days incarcerated during the intervention and follow-up phases;
- (3) Self-reported number of days of opioid and other drug use measured by TLFB, and objective measures of drug use by urine drug screens (UDS) at the 6-month post-release assessment (end of the intervention phase);
- (4) Self-reported days in drug abuse treatment;
- (5) Self-reported number of arrests;
- (6) Self-reported craving for opioids;
- (7) Self-reported number of overdoses; and
- (8) Self-reported motivation for treatment.

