8.0 STUDY ASSESSMENTS

Measures and instruments will be used to ensure a comprehensive assessment of status and functioning variables. These data, along with the DATCAP, will also be used to support the economic analysis. (The DATCAP will be administered during Year 2.) On average, screening and eligibility assessments will be completed in 4-6 hours (specific to treatment group). Post-release assessments will be completed in approximately 30-60 minutes. Medication Management visits are expected to take approximately 30-60 minutes.

Timepoints	Screening	Pre-	Post-release	
_		release		
Clinic Visits			Medical Mgmt	Assessments
				Months 1, 3,
				6, 7, 12
Measures				
Safety & Med. Measures				
Physical Exam / Med History	Х			
Injection site inspection	Х		X	
Vitals	Х		X	
12-lead ECG	Х			
Clinical Lab Tests	Х			
HIV Test	Х			
Pregnancy Test	Х		X	
Prior/Concomitant Meds	Х		X	
AEs			X	Х
Drug Use Measures				
DSM-5 Checklist	Х			
COWS (Withdrawal)	Х			
SOWS (Withdrawal)	Х			
Urine Drug Screen (UDS)	Х	Х	X	Х
Substance Use Report (TLFB)	Х	Х	X	Х
VAS (Craving)	Х	X	X	X
Crime and Recidivism				
Self-Report Arrest/Tx History			X	Х
Arrest Records				Х
CJ-DATS Crime Grid	Х			
HIV Risk Measure				
HIV-GAIN	Х			X
Cost				
Form 90				

Table	1. Data	Collection	Time and	Event	Schedule
I UDIC	I. Dutu	00110011011	This and		ouncaute

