8.3 Crime and Recidivism

8.3.1 Arrest Records

Arrest records will be accessed to compile information on participants' arrests, convictions, sentences, and incarcerations.

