10.3 Power and Sample Size

With the primary focus of this study on the feasibility and clinical utility of the two pharmacotherapies, the study is not powered to be an exhaustive comparison but to parsimoniously enable preliminary characterization of outcomes that will be needed to inform a future, larger scale multi-site trial. We expect that a baseline sample of 150 participants with 50 participants per condition will yield a final aggregate sample of approximately 120 participants. assuming 10-20% dropout. (Our similar studies have had 85-90% follow-up rates.) Thus, a final evaluable sample size of 120 participants would permit detection of a medium-large effect size (~.60) between conditions for some of the outcome variables (at ~.70 power) and .5 effect size (at .80 power) for others. For example, we expect that the measure "time to first opioid use" will be markedly different among the three groups, given the difference given the expected relapse among the no-medication group. Over time, the total number of opioid-free urine results is expected be greater among the VI participants, who are likely to show less dropout and better long-term retention compared to the DE group. Our selection of the effect size is based on effects found in the literature for Vivitrol when compared against placebo, and is consistent with both Cohen (1988) and with more recent guidance; for example, Lipsey and Wilson (1993) did a meta analysis of 302 meta-analyses that included over 10,000 studies and found that the average effect size was .5, adding support to Cohen's recommendation that selection of the effect size of .5 is appropriate (Bausell & Li, 2002).

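### Arrests and days incarcerated are defined by self-report only, although the trial already plans to obtain records of both; the records should be the named source, with self-report in support

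*Combined protocol and SAP*

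**What the plan says.** Secondary outcome (2) in Section 6.2 is "Self-reported number of days incarcerated during the intervention and follow-up phases", and outcome (5) is "Self-reported number of arrests". Sections 4.3.2 and 10.2 carry the same two definitions.

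The trial also plans an independent source. Section 8.3.1 states: "Arrest records will be accessed to compile information on" participants' "arrests, convictions, sentences, and incarcerations". Table 1 in Section 8.0 gives Arrest Records a row of its own, marked only under the post-release assessments (months 1, 3, 6, 7 and 12). A separate row, "Self-Report Arrest/Tx History", is marked under both medical management visits and assessments. The CJ-DATS Crime Grid is marked at screening only.

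Section 5.5 says of the university programs in the community: "These programs will be the locations for post-release assessment and medical management visits". No procedure is described for assessing someone who is back in custody. Section 7.14 makes the trial open-label.

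For missing data, Section 10.0 says both that post-baseline variables are left unimputed, relying on models under missing at random, and that outcomes other than the primary are multiply imputed. Section 10.4.1 adds case elimination and mean substitution as options. None of these rules refers to the records. On attrition, Section 10.3 expects that the sample of 150 "will yield a final aggregate sample of approximately 120 participants", "assuming 10-20% dropout".

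**The concern.** A self-reported count needs a participant who attends and answers. For these two outcomes the event can itself prevent attendance: someone held in jail, or avoiding arrest, cannot or may not come to a community clinic. If that person is not seen again, the arrest or custody after the last visit goes unrecorded. Among those who do attend, the report is given with knowledge of the assigned arm.

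Missingness that depends on the unseen event is not missing at random. A likelihood model or multiple imputation built on the attenders' data will tend to fill in too few events. The records named in Section 8.3.1 need neither attendance nor candour, yet they are given no role in the outcome definitions or their analysis.

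Reducing drug-related criminal activity is part of Aim 2 (Section 4.3), so these outcomes bear directly on a stated aim.

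**Working it through.** **Plan's own figure.** 150 × (1 − 0.20) = 120, which reproduces the evaluable sample in Section 10.3. At 10% dropout it is 150 × 0.90 = 135. Between 15 and 30 participants could therefore lack a complete self-report.

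**Understatement within one arm.** Let f be the fraction lost, L the event rate in those lost and S the rate in those seen. The true rate is f·L + (1 − f)·S, so the rate in those seen is too low by f × (L − S). The range for f comes from Section 10.3. The gap L − S is not in the documents; 30 to 50 points is an assumption.

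| Loss f | Gap 30 points | Gap 50 points |
|---|---|---|
| 10% | 3 points | 5 points |
| 20% | 6 points | 10 points |

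This is before any recovery through later visits or imputation. It concerns the proportion with any event, whereas the outcomes are counts of arrests and days, so it is an indication of scale only.

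**Bias in the contrast.** The error in the difference between arms is f₁·g₁ − f₂·g₂, where g is each arm's gap.

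- Loss of 10% and 20% with equal gaps of 30 to 50 points: the contrast moves by 3 to 5 points.
- Loss of 12% with a gap of 50 points and 20% with a gap of 30 points: 6 − 6 = 0, so there is no bias despite unequal loss.
- Loss of 15% in both arms with gaps of 50 and 30 points: 7.5 − 4.5 = 3 points, so there is bias despite equal loss.

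For scale, the standard error of a difference at 50 per arm, with proportions near 50%, is √(2 × 0.5 × 0.5 / 50) = 0.10, or 10 points.

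**Illustration with rates quoted in the protocol.** Section 4.1 cites a trial of oral naltrexone in probationers in which 56% of controls and 26% of treated participants were returned to prison within six months. Take these as true rates. Assume follow-up of 75% in those with the event and 95% in those without; neither figure is in the documents.

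- Overall follow-up: 0.56 × 0.75 + 0.44 × 0.95 = 0.838, and 0.26 × 0.75 + 0.74 × 0.95 = 0.898. These are close to the 85-90% that Section 10.3 reports for similar studies.
- Observed rates with fully honest reporting: 0.42 / 0.838 = 50.1%, and 0.195 / 0.898 = 21.7%. The arms are 5.9 and 4.3 points too low, and the difference falls from 30 to 28.4 points.
- If those who attend also report only 85% of events (assumed): 42.6% and 18.5%, a difference of 24.1 points.
- Over assumed follow-up of 60-85% in those with the event and reporting of 70-100%, the difference runs from 18.5 to 29.3 points.

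In the central case, under-reporting costs more of the difference (28.4 to 24.1) than loss does (30 to 28.4). The shrinkage towards zero follows from using the same follow-up and reporting rates in both arms. It is not a finding about this trial.

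**The case against.** The strongest reply is that a jailed participant need not be lost. Table 1 has five assessments out to month 12, Section 7.15 counts nine medical management visits, and arrest history is asked at both types of visit. Section 4.1.1 says jail stays tend to run from days to several months, so someone held at month 3 may report it at month 6, 7 or 12. Earlier visits also inform a model or an imputation. Exclusion 6 in Section 5.3.2 removes candidates whose pending legal action could interrupt participation. This stands in part: the whole count is lost only for those never seen again, and it would go too far to say that imputation can recover nothing. It does not remove the risk for those who stay away, nor the reliance on open-label report.

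Three further inferences are tempting but unsupported.

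- A reader might infer from Section 10.3 that loss will differ by arm. The remark there on dropout and retention explains an expected difference in opioid-free urines; it gives no assessment-completion rate by arm. Section 7.13 has those who stop medication continue with assessments.
- A reader might infer that unequal loss by itself biases the contrast. The arithmetic above shows that it need not.
- A reader might infer that the self-reported counts are what feed the savings estimates of Aim 3. Section 8.0 says that its measures, which include the records, support the economic analysis. Section 10.4.3 names no source for arrests, so that harm is not shown.

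It is also fair that these are two of eight secondary outcomes in a trial that Section 10.3 describes as preliminary, and that records may miss events elsewhere.

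**Conclusion.** The point holds as a low-cost improvement to two secondary outcomes; it does not touch the primary analysis. Both outcomes rest on self-report alone, records covering both are already planned, and the outcome and analysis sections leave those records unused. The counts are at risk of being missing or under-reported for participants who are re-arrested and not seen again, and the stated missing-data rules do not reliably correct this.

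The 3-10 point understatement per arm rests on the plan's 10-20% dropout, an assumed gap of 30-50 points and no recovery. The contrast is biased by differential loss only if the product of loss and gap differs by arm. Its size and direction cannot be settled from the documents.

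**What to change.** - In Sections 6.2 and 10.2 (and 4.3.2 to match), define outcomes (2) and (5) from arrest and incarceration records through months 6 and 12 for every randomised participant, regardless of visit attendance and within the consent given.
- Keep self-report as the supportive measure, and report agreement between the two sources by arm.
- State the record source and jurisdictions searched, the look-back window and whether it starts at randomisation or release, and the rule when the sources disagree. Confirm that the records give entry and release dates, so that days can be counted.
- Amend Table 1 so that record retrieval does not depend on an assessment visit.
- In Section 10.4.3, name the source used for arrests and re-incarceration.

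**Cost.** Collection is already planned, so this is mainly wording, plus a retrieval procedure for people who stop attending. Whether records may be searched after withdrawal depends on the consent text, which is not among the documents reviewed. Records can miss events outside the searched jurisdictions. Inclusion criterion 5 (planned local residence) limits this, and the retained self-report partly covers it. The change should be made before the data are analysed.

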2.4 Analyses

The primary outcomes include opioid use and DSM-5 diagnosis of opioid use disorder via modified CIDI-2 Substance Abuse Module at 6-months post-intervention. Opioid use will be computed from the Timeline Follow-Back (TLFB) as the number of days of self-reported opioid use in the past 30 days at the 6-month assessment. The cost analysis will measure and value resources associated with VI, including medical personnel (physician/nurses), labs, and medications. To ascertain cost-effectiveness ratios of VI and PNV, cost data will be compared to changes in key clinical measures of effectiveness.

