4.3 Objectives

The project emphasizes evaluation of the clinical utility of pharmacotherapy with Vivitrol (VI) or Vivitrol + PN (PNV) in comparison to a drug education (DE) condition. Descriptive statistics will provide an overall assessment of the implementation of the protocol. The aims of this project include:

Aim 1: Assess the feasibility and clinical utility of a 24-week protocol of long-acting naltrexone (by intramuscular *injection*; VI) provided with and without a PN component (VI, PNV). Measures include side effects, adverse events, retention, and acceptance of the procedures by participants and clinicians. Acceptance will also be assessed among correctional staff.

Aim 2: Examine the effectiveness of Vivitrol provided with and without a PN component (VI, PNV) for its ability to prevent relapse to illicit opioid use, reduce drug-related criminal activity, curtail engagement in HIV-risk behaviors, and increase employment compared to a group receiving only drug education (DE) to assist in relapse prevention after release from jail. The VI and PNV groups will receive VI monthly for the entire 6-month intervention phase. Th PNV group will be provided with PN for 3 months to provide assistance in accessing community treatment after release from jail. Primary measures include DSM-5 diagnosis at time to relapse (defined as self-report of daily opioid use for one week), protocol adherence, and opioid-negative urine samples during the study.

Aim 3: Collect cost data using the Drug Abuse Treatment Cost Analysis Program (DATCAP) and estimate savings from reduced drug use, reduced criminal activity and re-incarceration, and increased employment. Data will support benefit-cost and cost-effectiveness analyses of depot pharmacotherapy with Vivitrol for released offenders with opioid use disorders.

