7.3 Random Assignment

Eligible participants will be randomly assigned to study condition (VI, PNV, DE) in a 1:1:1 strategy using an urn randomization procedure (Stout et al., 1994) to provide multivariate balance across two characteristics correlated with outcomes in addiction treatment trials: type of opioid (heroin or prescription drug) and gender.

Individuals who terminate participation before induction onto the assigned medication (or similar time-point for behavioral assignments) will be replaced. Those terminating after VI induction or provision of the first DE session will not be replaced and will be counted as "treatment failures" (in an intent-to-treat scenario).

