7.4 Medication Pre-Induction

7.4.1 Vivitrol Pre-Induction

Vivitrol Pre-administration and Injection Procedures. Individuals must be free from opioids for at least 7 days before receiving the Vivitrol injection, which is confirmed via self-report and facility records. To ensure opioid abstinence at time of induction, a naloxone challenge will occur followed by one day of oral naltrexone before Vivitrol injection, adhering to NIDA-approved and IRB-approved procedures. Subsequent Vivitrol injections administered every four weeks will require confirmation of opioid abstinence by either naloxone challenge or administration of oral naltrexone, as determined appropriate and necessary by the Study Physician and/or Nurse Practitioner (NOTE: In New Mexico, a Nurse Practitioner [NP] has virtually all the same medical privileges as a Physician and can function as an Physician).

The pre-induction strategy includes:

- *Step 1.* Participants must self-report no clinically significant opioid use (i.e., at any level that could constitute a potential risk of precipitating opioid withdrawal upon naloxone administration in the next step) in the previous seven days.
- *Step 2.* A urine drug screen will be administered shortly before the naloxone challenge and must be negative for opioids. Individuals who are opioid-negative will continue in the pre-induction process. Individuals may have an additional urine drug screen on a subsequent day if the study medical clinician determines that a second screen is appropriate.
- *Step 3.* Completion of all pertinent psychosocial and medical screening and eligibility assessments.

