8.2 Drug Use Measures and Psychological Measures

8.2.1 Substance Use Report: Timeline Follow-Back (TLFB)

The TLFB will be used to elicit participants' self-reported use of alcohol and illicit substances. At screening, substance use reported by the participant for the prior 30-day period will be assessed. The TLFB will be administered at each study visit throughout the medication phase, at the post-medication visit, and at follow-up to document the participant's self-reported use of substances for each day since the previous assessment.

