8.2.2 Urine Drug Screen (UDS)

Urine samples will be collected at every clinic visit using FDA-approved one-step temperaturecontrolled urine drug test cups following all of the manufacturer's recommended procedures. The UDS will test for the presence of opiates, oxycodone, barbiturates, benzodiazepines, cocaine, amphetamines, MA, marijuana, methadone, and Ecstasy (MDMA). A validity check may be performed using a commercially available adulterant test strip that indicates normal ranges for creatinine, pH (at minimum), nitrate, glutaraldehyde, specific gravity, bleach and pyridinium chloromate. Study staff may observe the collection of UDS. In the event of suspected tampering, the study team will request a second sample and may observe the urine collection process according to clinic standard operating procedures.

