10.4 Analysis Approach

Analyses will employ modeling approaches that are less sensitive to biases from missing data, using a technique that conceptualizes missing data in two ways: intermittent missing data for participants active in the trial and dropouts (Shoptaw et al., 2002). Analysis of urine drug screen results are conducted using aggregates such as the Treatment Effectiveness Score (Ling et al., 1997), which is tested by condition using GLM and non-parametric strategies, where appropriate. Retention differences between conditions will be tested using an appropriate survival analysis model. Counts and composites of scores on drug craving and psychological measures will also be analyzed by treatment condition using t-tests and ANOVAs. Secondary analyses may include use of longitudinal models (Diggle et al., 1994), including normal mixed-effects models (Littell et al., 1996; SAS Institute, 1996; Singer, 1998; MIXED; PROC MIXED, SAS Institute Inc, Cary, NC) for continuous measures and generalized linear mixed models (Littell et al., 1996; GLMM; GLIMMIX macro, SAS Institute, Inc) for categorical measures. A six-step analysis approach is described below.

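### The urine panel has no test for buprenorphine, fentanyl or tramadol, so use of one of these alone can be recorded as opioid-negative in the trial's objective drug-use measure

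*Combined protocol and SAP*

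**What the plan says.** Section 8.2.2 gives the whole panel: "The UDS will test for the presence of opiates, oxycodone, barbiturates, benzodiazepines, cocaine, amphetamines, MA, marijuana, methadone, and Ecstasy (MDMA". Of these ten tests, three concern opioids (opiates, oxycodone, methadone). The section describes no confirmatory assay, cut-off or cross-reactivity.

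The result is used in four places:

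- Section 6.2, secondary outcome 3: "objective measures of drug use by urine drug screens (UDS) at the 6-month post-release assessment (end of the intervention phase".
- Section 4.3, Aim 2, which lists "opioid-negative urine samples during the study" among its primary measures.
- Section 10.4, where urine results are analysed through "aggregates such as the Treatment Effectiveness Score".
- Section 7.4.1, Step 2, before the first injection: "A urine drug screen will be administered shortly before the naloxone challenge and must be negative for opioids".

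Section 7.3 balances the urn randomisation on "type of opioid (heroin or prescription drug) and gender", so users of prescription opioids are expected. No section says which strips make a sample opioid-negative, or how an opioid outside the panel is handled.

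The primary outcomes come from elsewhere. Section 2.4 (Analyses) states: "Opioid use will be computed from the Timeline Follow-Back (TLFB) as the number of days of self-reported opioid use in the past 30 days". Under Section 8.2.4 the diagnosis comes from the DSM-5 checklist or the modified CIDI.

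**The concern.** By listing oxycodone and methadone separately, the plan shows that it does not rely on the opiates strip to catch every opioid. Buprenorphine, which Section 4.1.2 itself classes with methadone as an opioid agonist, has no strip. Neither do fentanyl and tramadol. Someone whose only recent opioid is one of these can be scored as opioid-negative, and nothing in the plan would reveal it.

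The trial is open-label (Section 7.14) and its opioid-use outcome is self-reported, so urine is the biological check on that self-report. The check is weakest for opioids without a strip. Its result also depends on which opioid was taken: methadone counts as positive and buprenorphine may not, whether or not either was prescribed.

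**Working it through.** **1. Document comparison.**

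| Item | Section | Content |
|---|---|---|
| Opioid tests on the panel | 8.2.2 | opiates, oxycodone, methadone (3 of 10) |
| Not on the panel | 8.2.2 | buprenorphine, fentanyl, tramadol |
| Opioid users expected | 7.3 | heroin and prescription drug |
| Construct measured | 6.2, 4.3 | objective drug use; opioid-negative urine |
| Rule linking strips to the construct | none found | not stated |

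The construct is broader than the panel, and no rule bridges the two.

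**2. Size, as an illustration.** The plan gives no missed share and no urine-outcome power figure, so there is nothing to reproduce. Inputs:

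- n = 40 per arm: 120 evaluable over three arms (Section 10.3).
- Two-sided 0.05 (Section 10.0).
- True positive rates of 30% and 8%. Section 4.1 reports these as mean percentages of positive urine tests in a trial of oral naltrexone in probationers. Treating them as proportions of participants positive is an assumption.
- m, the share of true positives missed: an assumption, 0 to 30%, equal in both arms.

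The observed rates are p1 = 0.30(1 − m) and p2 = 0.08(1 − m). With p̄ their mean,

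power = Φ{ [ (p1 − p2) − 1.96·√(2p̄(1 − p̄)/n) ] / √( [p1(1 − p1) + p2(1 − p2)]/n ) }.

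At m = 0: p̄ = 0.19; null SE = √(2 × 0.19 × 0.81/40) = 0.0877; alternative SE = √((0.21 + 0.0736)/40) = 0.0842; (0.22 − 0.1719)/0.0842 = 0.571; power = 0.716.

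| m | Observed rates | Risk difference | Risk ratio | Power |
|---|---|---|---|---|
| 0 | 0.300 v 0.080 | 0.220 | 0.267 | 0.716 |
| 5% | 0.285 v 0.076 | 0.209 | 0.267 | 0.687 |
| 10% | 0.270 v 0.072 | 0.198 | 0.267 | 0.658 |
| 20% | 0.240 v 0.064 | 0.176 | 0.267 | 0.595 |
| 30% | 0.210 v 0.056 | 0.154 | 0.267 | 0.528 |

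With assumed rates of 50% and 30%, power falls from 0.445 at m = 0 to 0.283 at m = 30%.

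The factor (1 − m) cancels from the risk ratio. It does not cancel from the odds ratio, which moves from (0.08/0.92)/(0.30/0.70) = 0.203 to (0.056/0.944)/(0.21/0.79) = 0.223 at m = 30%. That is a small shift towards 1.

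The expected positives at m = 0 are 12 and 3.2, so the normal approximation is rough. The calculation models a single binary comparison, not the aggregate score of Section 10.4.

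**3. Prescribed medication.** Section 2.4 (Interventions) refers all arms to community treatment, and Aim 2 concerns illicit use. Counting any positive strip as relapse would therefore count prescribed methadone, and prescribed buprenorphine once a strip is added. This would probably happen more often in drug education than in the two arms receiving an antagonist; that is an inference, not a documented rate. Section 8.1.6 (Prior and Concomitant Medications) already collects the data needed to separate these cases. Table 1 schedules that form at screening and at medical management visits, but not in the assessment column.

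**The case against.** The strongest reply is that relevance is not shown. The documents do not mention fentanyl or tramadol, present buprenorphine as a treatment rather than a drug of relapse, and give no prevalence or cross-reactivity. This stands: under-detection is possible, and its amount is unknown.

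Section 10.3 also says that the study is not powered for an exhaustive comparison, and secondary outcome 3 pairs urine with the TLFB. The TLFB covers "self-reported use of alcohol and illicit substances" and is not tied to the panel. Both points limit the consequences, but self-report cannot serve as its own objective check.

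A further reply is that a broader panel with a crude positivity rule could bias the arm comparison, by scoring prescribed treatment as relapse. That is correct and shapes the fix. The plan already has the same problem for methadone, without a rule.

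Four stronger readings are tempting and are not supported:

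- *That no synthetic opioid is tested.* Methadone is one, and it is on the panel.
- *That the loss falls mostly on prescription-opioid users.* No figure shows this, and oxycodone and methadone both have strips.
- *That the primary results are compromised.* Neither primary outcome in Section 6.1 comes from urine. Aim 2 calls opioid-negative urines a primary measure, but Sections 6.1 and 10.1 do not.
- *That later injections rest on the urine screen alone.* Section 7.4.1 requires abstinence to be confirmed by naloxone challenge or oral naltrexone, and its Step 4 says that a negative urine is not proof.

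**Conclusion.** The point holds for the urine outcomes. As written, the plan can record use of buprenorphine, fentanyl or tramadol alone as opioid-negative, and it does not define opioid-negative. If 10% to 30% of positives were missed equally in both arms, power in the 30% versus 8% illustration would fall from about .72 to between .66 and .53, and the risk difference from 22 points to between 19.8 and 15.4. The risk ratio would not change. These figures rest on assumed rates, an assumed missed share and a simple two-proportion test. Bias in the risk ratio would need detection to differ by arm, which the documents do not show. This is an inexpensive improvement to the objective measure, not a defect in the primary analysis.

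**What to change.** For the outcome measure in Section 8.2.2:

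1. Use, in all arms and from the first participant, an FDA-approved one-step cup that adds a buprenorphine strip, and a fentanyl strip if such a cup can be sourced. Availability cannot be judged from the documents.
2. Report results per strip.
3. Define an opioid-positive outcome as any opioid strip positive that is not explained by medication prescribed and recorded on the concomitant-medication form. Add a sensitivity analysis counting every positive strip, because the rule depends on that form being complete.
4. Complete the form at any assessment visit that contributes a urine outcome and has no medical management visit alongside.
5. If the panel stays as it is, label the outcome *negative for opiates, oxycodone and methadone*. Any opioid left without a strip should be stated as a limitation.

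**Cost.** The sample, visits and staff are unchanged. The price per cup is higher, for at most 16 samples per participant (1 screening + 1 pre-release + 9 medical management + 5 assessments; fewer where visits coincide). There is also a short form at a few visits.

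These changes concern outcome scoring only. The protocol should state separately how they relate to the pre-induction screen, which is a clinical matter. Sections 7.4.1 (opening text and Step 4) and 11.23 also differ on whether a naloxone challenge precedes each later injection. Those passages must be reconciled, and this review takes no position on which should stand.
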